
Secondary endpoints
	
Secondary endpoints will be measured continuously up to 28 days after enrollment.
 
The secondary endpoints will assess ventilation safety and efficacy by measuring physiological variables, clinical outcomes, and associated interventions continuously up to 28 days after enrolment.
 
Efficacy
 
Physiologic parameters:
 
 1) Respiratory mechanics (Compliance, resistance, expiratory time constant) will be assessed automatically breath-by-breath 2) Oxygenation ($\text{PaO}_2/\text{FiO}_2$, FiO_2, PEEP) 3) Ventilation (VT, RR, mechanical power will be assessed automatically breath-by-breath, ΔP, P_{PLAT}, will be assessed twice a day). 4) FiO_2 levels to be assessed in both study arms 
Outcomes:
 
 1) Duration of invasive mechanical ventilation: time between intubation and last extubation or death. When a subject is re-intubated within 48 hours after extubation, the period between extubation and re-intubation is considered as invasive ventilation days. 2) Duration of non-invasive mechanical ventilation: noninvasive ventilation (NIV) refers to Continuous Positive Airway Pressure (CPAP) or pressure support NIV delivered before intubation or after extubation. High flow therapy is not considered in this calculation. 3) Total duration of mechanical ventilation: sum of duration of invasive and noninvasive mechanical ventilation. 4) Time from intubation to first successful Spontaneous Breathing Trial (SBT) 5) Passive ventilation duration: passive ventilation is defined when the percentage of subject's triggered breath is lower than 25% of total respiratory rate. 6) Weaning duration: time between the first sedation cessation to the last extubation or the last disconnection from the ventilator for tracheostomized subjects. Subjects reintubated within 48h after extubation will be kept in the study. Subject that are re-intubated beyond 48h will be considered as weaned from the ventilation.
-----------------------------------	---

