	
7) Ventilator free days (VFD) up to day 28: VFD to day 28 are defined as: the number of days from the time of initiating unassisted breathing to day 28 after start of ventilation, assuming survival for at least 48 hours and no re-intubation within 48 hours after initiating unassisted breathing and continued unassisted breathing to day 28.
 
NIV will be considered as assisted breathing. CPAP will not be considered as assisted breathing. Ventilator free days will be calculated separately for invasive ventilation support and any other ventilation support (invasive and noninvasive).
 
If a subject returns to assisted breathing (re-intubated within 48 hours) and subsequently achieves unassisted breathing to day 28, VFDs will be counted from the end of the last period of assisted breathing to day 28.
 
A period of assisted breathing lasting less than 24 hours and for the purpose of a surgical procedure will not count against the VFD calculation.
 
If a subject was receiving assisted invasive breathing on day 27 or dies prior to day 28, VFDs will be -1.
 
For subjects transferred to another hospital or other health care facility, study data collection will be stopped but subject will be contacted via a phone call on day 28 post enrollment to assess VFD endpoint if possible:
 
• ICU and hospital length of stay (discharge).• ICU mortality (if the subject is hospitalized in another hospital than the investigational site)• Non-intensive ventilation (NIV) duration• 28 days mortality• Ventilation duration for study period (if reintubated beyond 48h)• Tracheostomy
--	---

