Ventilatory parameters manual assessment		X	X	X	X	X	X	X	X	X	X	X	X	X	X	X
24h Recording of ventilation parameters *(Memory Box)		X	X	X	X	X	X	X	X	X	X	X	X	X	X	X
Blood gas analysis (If available visit $\pm 2h$)	X	X#	X	X	X	X	X	X	X	X	X	X	X	X	X	X
ICU severity Scores (SAPS II, APACHE II)					X											
SOFA score						X			X			X				X
Concomitant sedation, analgesia and myorelaxants use		X	X	X	X	X	X	X	X	X	X	X	X	X	X	
Concomitant vasopressors and inotropics use		X		X	X	X	X	X	X	X	X	X	X	X	X	

Study Period	Intervention Period														End of Study	Study Exit
	Time	Day 0	Screening	Baseline	Day 0	Day 0	Day 1	Day 1	Day 2-3	Day 4	Day 4	Day 5-6	Day 7	Day 7	Day 8-27	
Time specifications		T0	T0+1h	T0+6h (only if T0 before 12 a.m.)		morning visit time + at least 6h			mornig visit time + at least 6h			morning visit time + at least 6h			Day XX	Day 28
Visit #	Visit 1	Visit 2	Visit 3	Visit 4	Visit 5	Visit 6	Visit 7-10	Visit 11	Visit 12	Visit 13-16	Visit 17	Visit 18	Visit 19-59	Visit 60	Visit 61	
Number of recruitment maneuvers within the last observation period				X	X	X	X	X	X	X	X	X	X	X		
Concomitant rescue therapies (proning, Nitric oxyde, ...)		X		X	X	X	X	X	X	X	X	X	X	X		
Weaning information NIV, CPAP, High Flow.)				X	X	X	X	X	X	X	X	X	X	X		
Screening of readiness to extubate criteria (SBT)						X	X	X	X	X	X	X	X	X		
Assessment of re-intubation status							X	X	X	X	X	X	X	X		
Extubation failure (yes/no)							X	X	X	X	X	X	X	X		
Acute Kidney Injury (AKI) status and need vor RRT (yes/no)	X	X						X		Xf	X			Xf	X	X
Criticall illess polyneuro- myopathy status (yes/no)	X	X						X		Xf	X			Xf	X	X
Criticial illess encepaehlopathy status (yes/no)	X	X						X		Xf	X			Xf	X	X
Tracheostomy status (yes/no)											X			Xf	X	X
Resuscitated cardiac arrest status (yes/no)								X			X					X
Other imminently life-threatening experience								X			X					X
Barotrauma status (yes/no)								X			X					X
Rescue therapy requirement (APRV, HFO, ECCO2R and ECMO).																X
Patient status incl. Withhold of weaning and/or withdrawald of MV															X	X**
Ventilation duration for study period (if reintubated beyond 48h)															X	
ICU and hospital length of stay															X	X**
ICU/Hospital death															X	X**

Study Period	Screening	Baseline	Intervention Period												End of Study	Study Exit
			Day 0	Day 0	Day 0	Day 1	Day 1	Day 2-3	Day 4	Day 4	Day 5-6	Day 7	Day 7	Day 8-27	Day XX	Day 28

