8.3.4 Measurements

Breath-by-breath ventilation variable will be recorded during the full duration of study period.

On top of that, ΔP , P_{plat} , total PEEP, and blood gas results (if performed) will be measured twice a day and reported on the eCRF.

Information of acute pulmonary condition will be recorded in the eCRF.

Information about controllers de-activation and weaning process will be reported on a daily basis on the eCRF.

All concomitant medications will be recorded in the eCRF including sedation.

8.4 End of study (extubation + 48 hours):

The end of study visit should be completed at the time a subject completes the study ventilation protocol. It means that the subject is extubated and there is no need for re-intubation within 48 hours.

Subject reintubated within 48h after extubation will continue to be ventilated per the allocated randomized ventilation mode.

Subject re-intubated beyond 48h will be considered as weaned for the ventilation procedure. They remain in the study but only a phone call will be done on Day 28.

Following data point to be collected and recorded:

- Intubation/ re-intubation status
- Acute Pulmonary Condition
- Vital Signs
- Ventilator parameters manual assessment
- 24h Recording of ventilation parameters (Memory Box)
- Blood gas analysis (If available visit $\pm 2h$)
- SOFA score
- Concomitant sedation, analgesia and myorelaxants use
- Concomitant vasopressors and inotropics use
- Number of recruitment maneuvers within the last observation period
- Concomitant rescue therapies (proning, Nitric oxide, ...)
- Weaning information associated interventions (Patient Passive/Active but still on MV, NIV, CPAP, High Flow.)
- Screening of readiness to extubate criteria (SBT)
- Assessment of re-intubation status

- Extubation failure
- Acute Kidney Injury (AKI) status and need for RRT
- Critical illness polyneuro- myopathy status
- Critical illness encephalopathy status
- Tracheostomy status
- Resuscitated cardiac arrest status
- Other imminently life-threatening experience
- Barotrauma status
- Rescue therapy requirement (APRV, high frequency ventilation, ECCO₂R and ECMO).
- Withhold of weaning and/or withdrawal of mechanical ventilation status
- Ventilation duration for study period (if reintubated beyond 48h)
- ICU and hospital length of stay
- ICU mortality (if subjects hospitalized somewhere else) or 28 Days mortality
- Adverse Event collection

8.5 Study Exit (Day 28):

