Prior to completion of study close out, all subject data must be captured and monitored in the eCRF.

A subject will be considered to have completed the study for the following reasons:

- Subject completes follow-ups (Day 28) required per investigational plan.
- Subject dies.
- Subject or legally authorized representative requests to be withdrawn from the study.
- Investigator requests to be withdrawn from the study to protect the welfare of the subject. (In that case, it is at the site's principal investigator's discretion to determine that the study is no longer in the subject's best interest.)

In case of sponsor's decision to stop the study, the site will be notified by the sponsor in written of the intention to close the study. Study close out visits are then to be performed. During these visits, the monitors will ensure that the investigator's regulatory files are up to date and complete and that any outstanding issues from previous visits have been resolved. The site will be informed that all requirements have been met with a study closure letter.

Following data point to be collected and recorded:

- Intubation status
- Acute Pulmonary condition
- Extubation failure - with SBT
- Acute Kidney Injury (AKI) status and need for RRT

- Critical illness polyneuro- myopathy status
- Critical illness encephalopathy status
- Tracheostomy status
- Ventilation duration for study period (if reintubated beyond 48h)
- ICU and hospital length of stay
- ICU mortality
- Adverse Event collection

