4.4 Subgroup Definitions

Forest plots will be used to display results of primary endpoints and total duration of MV within the following subgroups listed below:

- Regions (US vs Europe)
- Study centers
- Gender

All efficacy tables and forest plots displaying primary and tertiary efficacy results will also be presented by treatment arm and for four groups based on subject condition at inclusion:

- Normal lungs
- ARDS
- Chronic Hypercapnia
- Brain injury

Additionally, forest plots to display primary and tertiary efficacy results by spontaneous and passive breathing subjects for the six ventilation and oxygenation variables will be reported:

1) Tidal volume (VT)

- 2) Maximum pressure (Pmax)
- 3) Oxygen saturation measured by pulse oximetry (SpO₂)
- 4) End-tidal partial pressure of carbon dioxide (PetCO₂)
- 5) Respiratory rate (RR) for spontaneous breathing subjects
- 6) Pmax-PEEP for passive ARDS subjects

Study centers will be pooled from largest to smallest until the pooled center had more than 5 subjects in each treatment group.

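### Any-support ventilator-free days, NIV duration and total ventilation duration run to Day 28, but no scheduled item records NIV after the End of Study visit except for transferred subjects

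*Protocol*

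**What the plan says.** **Endpoints.** The synopsis states: "Secondary endpoints will be measured continuously up to 28 days after enrollment". Three secondary outcomes depend on NIV (synopsis; protocol 5.2; SAP 3.2.2):

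- NIV duration, which covers NIV before intubation or after extubation and has no stated end.
- Total duration of mechanical ventilation, the sum of invasive and non-invasive time.
- VFD to Day 28, in two versions: "Ventilator free days will be calculated separately for invasive ventilation support and any other ventilation support (invasive and noninvasive". For VFD, "NIV will be considered as assisted breathing", CPAP is not, and unassisted breathing has to last to Day 28.

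Protocol 8.3.1 D permits NIV after extubation. SAP 4.4 says: "Forest plots will be used to display results of primary endpoints and total duration of MV" by region, centre and gender.

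**Collection.** The NIV row in both schedules is "Weaning information NIV, CPAP, High Flow". It is marked up to the End of Study visit and blank at Day 28. Protocol 8.4, headed extubation + 48 hours, says: "The end of study visit should be completed at the time a subject completes the study ventilation protocol". The Day 28 list in 8.5 has intubation and tracheostomy status, length of stay, mortality and one ventilation-time item, "Ventilation duration for study period (if reintubated beyond 48h"). It has no NIV item. For subjects transferred to another facility, the Day 28 phone call does include "Non-intensive ventilation (NIV) duration".

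**The concern.** An outcome defined to Day 28 needs data to Day 28. Invasive support has them, because intubation status is scheduled at study exit. NIV does not, unless the subject was transferred.

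The any-support VFD is the version that could show whether time gained off the tube is later spent on NIV. If late NIV is unrecorded, it cannot show this in either arm. Total duration of mechanical ventilation, the only secondary outcome that SAP 4.4 names for its region, centre and gender forest plots, is cut short in the same way. The observation window also depends on where a subject was discharged: to Day 28 for those transferred, to End of Study for the rest.

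**Working it through.** The plan gives no figure to reproduce, so the check sets definitions against collection and then works an illustration.

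**Step 1. Definition against data source**

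| Quantity | Needed to | Scheduled source | Last scheduled record |
|---|---|---|---|
| Invasive support | Day 28 | Intubation/reintubation status | Day 28 |
| NIV, non-transferred | Day 28 | Weaning information row | End of Study (protocol Visit 60, SAP Visit 61) |
| NIV, transferred | Day 28 | Phone call | Day 28, as a duration without dates |

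The visits for Days 8 to 27 carry the NIV row, but they belong to the intervention period. Protocol 8.3.1 and SAP 4.1.1 run that period up to extubation without re-intubation within 48 h. The Day 28 ventilation-duration item is conditional on late re-intubation, so it does not reach a subject whose only late support is NIV.

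**Step 2. Which NIV is missed**

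The end of follow-up for the NIV item is stated in two ways.

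- Protocol 8.3.1 D (repeated in 8.3.2 C and SAP 4.1.1): the ventilator protocol continues until the subject breathes unassisted for 48 h. Since NIV is assisted breathing for VFD, NIV running on from extubation would delay this end and be recorded. NIV begun after 48 h unassisted is missed. ICU discharge is also listed as an end, so ward NIV after it has no scheduled item.
- Protocol 8.4: the end is extubation with no re-intubation within 48 h. NIV continuing past that point is then missed as well.

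A gap remains under either rule; only its width changes.

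**Step 3. Effect on one subject (dates assumed, ventilation started Day 0)**

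Let E be the extubation day and L the day the last NIV episode ends.

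- VFD from the collected data = 28 − E
- VFD by the definition = 28 − L
- Over-count = L − E

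With E = 5 and NIV from Day 10 to Day 14, which lies beyond both end rules:

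- Collected: 28 − 5 = 23
- By definition: 28 − 14 = 14
- Over-count: 14 − 5 = 9 days
- Lost from NIV duration and from total duration: 14 − 10 = 4 days

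The largest possible over-count is 28 − E: 26, 23 or 20 days for extubation on Day 2, 5 or 8.

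**Step 4. Effect on an arm mean (late-NIV rates assumed)**

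Inflation of mean VFD = proportion with late NIV × over-count.

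- 9-day over-count: 5% gives 0.05 × 9 = 0.45 day; 10% gives 0.9; 20% gives 1.8.
- Over-counts of 5 to 15 days: from 0.05 × 5 = 0.25 to 0.20 × 15 = 3.0 days.
- Loss in mean NIV and total duration at 4 days per affected subject: 0.05 × 4 = 0.20 to 0.20 × 4 = 0.80 day.

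The bias in the between-arm difference is the difference of the two arms' inflations. It is zero if they are equal. With 10% in one arm and 5% in the other, at 9 days each, it is 0.9 − 0.45 = 0.45 day in favour of whichever arm has more late NIV.

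**Step 5. Does a missing-data rule cover it?**

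SAP 4.8 provides multiple imputation for secondary outcomes where necessary. Unrecorded NIV does not show as missing; it looks like no NIV. The only written VFD reset concerns re-intubation within 48 h.

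**The case against.** Several points on the other side carry weight.

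- **Not all post-extubation NIV is lost.** Under the 48 h unassisted rule, NIV running on from extubation is still recorded. This stands, and limits the certain part of the gap to NIV begun after that period.
- **The scoring is inferred.** No text says that late NIV counts as ventilator-free, and the plan asks for secondary outcomes to be recorded up to 28 days. True, but no scheduled item supplies another value and no rule provides for late NIV.
- **The CRF may hold a field.** The SAP cites CRF Version 6.0, which is not among the documents, and hospital charts are source documents. A start/stop field cannot be excluded. Even so, the protocol and SAP schedules should require it.
- **Table 1 is weak evidence alone.** Some of its rows are not cleanly aligned in the protocol text. SAP Appendix 1 and the written list in 8.5 agree with the reading used here.
- **Bias toward the device.** A reader might infer this because the INTELLiVENT-ASV arm weans with an automated tool. The documents do not support it. The collection rule, extubation criteria and permitted post-extubation support are common to both arms, and nothing shows that one arm extubates earlier and then uses more late NIV.

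**Conclusion.** The mismatch holds. For non-transferred subjects, three secondary outcomes defined to Day 28 rest on an NIV item that ends at End of Study. At the least, NIV begun after 48 h of unassisted breathing is not captured; if 8.4 governs, NIV continuing past extubation + 48 h is not captured either. By default both would count as ventilator-free. Transferred subjects have a different ascertainment window.

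An affected subject's any-support VFD can be wrong by several days (9 in the illustration). The effect on an arm mean, 0.25 to 3.0 days over the ranges tried, rests wholly on assumed late-NIV rates and over-counts. The size of any between-arm bias cannot be derived from the documents, and its direction is unknown. The conclusion assumes that the CRF follows the published schedules.

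It would be wrong to extend this to the co-primary endpoints or the invasive-only VFD, which do not use NIV data. This should be corrected, but it does not threaten the primary analysis.

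**What to change.** 1. Add to protocol 8.5 and to the Study Exit column of Table 1 and SAP Appendix 1, for all subjects including those transferred: NIV and CPAP since extubation, recorded separately, with start and stop dates, from the chart or the Day 28 contact. Dates are needed because a duration does not give the end of the last assisted period. The two types must be separate because CPAP counts in NIV duration but not as assisted breathing for VFD.
2. Compute NIV duration, total duration and any-support VFD from these dates. State in SAP 3.2.2 that the any-support VFD counts from the end of the last NIV or invasive period.
3. Reconcile the end rules in protocol 8.3.1 D and 8.4, and carry the result into SAP 4.1.1.
4. Where late NIV cannot be recovered, report NIV and total duration as observed to End of Study. Do not present any-support VFD to Day 28 as if late NIV had been ascertained; treat it as missing or flag the limitation. Relabelling the VFD to an End of Study window is no substitute, because a count to Day 28 loses its meaning there.

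The cost is one block of eCRF fields at an existing contact, plus a chart look-back for subjects who have already exited. There is no new visit and no change to the co-primary analyses.

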1.3 Investigational Site(s)

Investigational sites will be located both in Europe and in US.

The list of sites with contact details of the study team and principal investigators is maintained in the Trial Master File and provided to the investigators.

1.4 Statistician ("Biostatistician")

An independent blinded statistician from IDDI will be in charge of optimizing the study design and performing the statistical analysis.

1.6 Data Safety Monitoring Board

A Data Safety Monitoring Board (DSMB) will be settled by the sponsor and will be composed experts in mechanical ventilation independent from the study coordinators and investigators.

The responsibility of the DSMB is to evaluate safety data during the course of the trial and to advise Hamilton Medical about the continuing safety of the Study.

Listings of recorded Adverse Events/Serious Adverse Events and Device Deficiencies will be provided by VCLS VigOps to the Independent Medical Monitor to evaluate safety of the study device. All events,

including any device related events will be reviewed on a case by case base by the Independent Blinded Medical Monitor. A safety concern raised by the Independent Medical Monitor triggers a DSMB meeting. Trial data will be reviewed on a periodic basis as defined in the DSMB Charter.

Based on the available safety data, the DSMB may recommend that Hamilton Medical modify or terminate the trial. DSMB composition, duties, procedures, deliberation rules are detailed and documented in the DSMB Charter.

2 ETHICAL AND REGULATORY ASPECTS

2.1 Study registration

Study is registered at ClinicalTrials.gov, ClinicalTrials.gov Identifier: NCT04400643.

Study registration in any other databases that might be required per local requirements/regulations will be done by the sponsor or designee.

2.2 Institutional Review Board (IRB) / Independent Competent Ethics Committee (EC)

It is the responsibility of the investigator and of Hamilton Medical to have prospective approval of the study protocol, protocol amendments, informed consent forms, and other relevant documents, e.g., recruitment advertisements, if applicable, from the IRB/EC. All correspondence with the IRB/EC should be retained in the Investigator Site File. Copies of IRB/EC approvals should be forwarded to Hamilton Medical.

The only circumstance in which an amendment may be initiated prior to IRB/EC approval is where the change is necessary to eliminate apparent hazards to the subjects. In that event, the investigator must notify the IRB/EC and Hamilton Medical in writing immediately after the implementation.

2.3 Competent Authorities (CA)

Competent authorities will be notified prospectively by Hamilton Medical as need be. The sponsor, Hamilton Medical, will be ultimately responsible for ensuring that competent authorities' approvals are approved in target countries.

2.4 Ethical Conduct of the Study

The study will be carried out in accordance to the protocol and with principles enunciated in the current version of the Declaration of Helsinki (2013), the guidelines of Good Clinical Practice (GCP) issued by ICH and in accordance to local regulation law.

2.5 Declaration of interest

Site investigator will complete financial disclosure form (Form 3455), 21 CFR Part 54.

2.6 Suspension or Premature Termination of the Clinical Investigation

This study may be discontinued at any time by Hamilton Medical, the US FDA, OHRP, other government or regulatory authorities, or site IRB(s)/EC(s).

The Sponsor may decide to stop the study early or close a site in the following situations:

- If the Sponsor received information about the Investigational device which is liable to change the benefit/risk balance;
- In the event of inadequate recruitment within the predetermined time on the site;
- If the Investigator received information about the investigational device or resources that may jeopardize the conduct the study;
- If the Sponsor considers that the results of the Clinical Study are not scientifically convincing;
- If the objective of the study is no longer relevant or of interest;
- If the Investigator fails to meet of his/her fundamental obligations through the terms of this agreement, and particularly a breach of the Clinical Study Protocol, a breach of the current laws and regulations or a breach of Good Clinical practices requirements;
- If the total number of subjects recruited is achieved earlier than planned;
- If it is a regulatory decision;
- If the Sponsor agrees with DSMB/ Medical Monitor's recommendation to terminate the Study based on site recorded AE(s)/SAE(S).

In all situations, the Sponsor will inform the Investigator of its decision in writing.

If an investigational site is suspended or prematurely terminated:

- The investigator shall then promptly inform enrolled subjects
- The investigator agreement will be terminated
- The investigator will inform the institution
- Sponsor will inform the Regulatory Authority(ies) (where required by applicable regulatory requirements)

When the risks are found to outweigh the potential benefits or when there is conclusive proof of definite outcomes, investigators must assess whether to continue, modify or immediately stop the clinical study in the respective investigation site and immediately inform the sponsor and IEC/IRB, if applicable.

